8.2. Subject Enrollment

A subject is considered enrolled in this clinical study at the time at which he/she signed and dated the ICF. The investigator will maintain a log of all subjects enrolled in the clinical investigation, assigning an identification code linked to their names, alternative subject identification or contact information.

8.3. Inclusion Criteria

All of below inclusion criteria must be met:

- Patient referred to the center to undergo ablation of the pulmonary vein using radiofrequency (initial AF ablation or redo procedure).
- In case of paroxysmal AF, the right atrium should be dilated as indicated by $> 29 \text{ ml mm}^2$ or the left atrium should be dilated as indicated by $> 34 \text{ ml mm}^2$.
- Patient is willing and able to cooperate with the study procedure.
- Patient is willing to provide the Informed Consent for their participation in the study.

8.4. Exclusion Criteria

None of the below exclusion criteria must be met:

- Patients under 18 years or over 80 years old.
- Women who are currently pregnant or have a positive pregnancy test.
- Patients with an implantable cardiac device
- Patients who already underwent an AF septal ablation procedure.

9. Study preparation

9.1. Investigator/Investigation site selection

An investigator/investigation site may be included in the investigation if the investigator/investigation site complies with the following requirements:

- Investigator/site is qualified by training, education, and relevant experience appropriate to the use of the product and associated procedures
- Investigator/site expects to have adequate time and resources to conduct the study throughout the duration of the study
- Investigator/site has access to an adequate number of eligible subjects
- Ability to comply with applicable Ethics Committee (EC) and regulatory requirements (if applicable)
- Investigator is not debarred, disqualified, or working under sanctions in the applicable region

At time of study protocol definition no investigator/investigation site have been already selected, so the complete list of participating investigators/investigation sites, including their details, will be provided under a separate cover once investigator/investigation site selection will be completed.

9.2. Site activation

Before performing study related activities, all requirements shall be fulfilled, including, but not limited to the following:

- EC approval (and voting list, as required by local law) of the current version of the CIP and ICF.
- Regulatory Authority approval or notification (as required per local law)
- Fully executed Clinical Trial Agreement (CTA)
- Curriculum Vitae (CV) of investigators and key members of the investigation site team

- Documentation of delegated tasks
- Documentation of study training.

Additional requirements imposed by the EC and Regulatory Authority shall be followed, as appropriate.

Medtronic may distribute pre-populated study-specific ISF and will provide site with documentation of study site/investigator readiness. Evidence of site/investigator readiness must be received prior to subject enrollment and must be filed in the ISF.

10. Study Procedures

Baseline:

Patients will be pre-screened for potential enrolment in the clinical investigation by evaluating if the patients meet the inclusion and exclusion criteria. Next the patient is asked for her or his informed consent. A patient is considered an enrolled subject after he/she has personally signed and dated the ICF. At baseline, subject characteristics will be noted such as age, gender, weight, height, AF status and AF history.

Enrolled subjects will undergo the AF ablation procedure, for which they have been referred to the center. For this standard procedure, the subject will be prepared as per standard catheterization/EP procedures, which includes administration of anesthesia/analgesia, ECG and BP monitoring.

Procedure:

The subject will be sedated. A trans-septal puncture will be made to access the left atrium and place a septal catheter and the clinically used ablation catheter. One decapolar recording catheter will be placed in the right atrium and one decapolar recording catheter will be placed in the coronary sinus. Both decapolar catheters are used according to standard clinical practice. The standard procedure workflow is visualized on the left side of figure 1 below.

After successful pulmonary vein isolation, there is a routine waiting time of half an hour to confirm efficacy of the ablation procedure. During this waiting period, the study procedure will be performed. The deviations from the standard procedure are indicated in orange on the right of figure 1 below. The septal catheter, already in place in the right atrium, will be positioned on the left interatrial septum via a trans-septal approach. In most cases the patient will be in sinus rhythm. In these cases, during sinus rhythm pacing thresholds and impedances on all septal catheter electrodes will be determined. Also, potential ventricular capture will be assessed. Next, atrial fibrillation will be induced by rapid atrial pacing. AF cycle length will be determined, during 1 minute of atrial fibrillation using the ablation catheter electrodes. Subsequently, the rapid pacing phase of the two-stage atrial pacing scheme will be applied to four septal electrodes at same time during half a minute using the quadripolar electrophysiological stimulator (e.g. EP4 stimulator). An electrophysiological recording system (already in place for the AF ablation procedure), recording all atrial electrograms, will be used to assess the study

[figure not shown]
outcome of local atrial capture. In addition, if feasible, AF termination will be evaluated using the two-stage pacing algorithm. If needed cardioversion will be used to terminate AF.

In a minority of cases the subject will still be in AF after successful pulmonary vein isolation. In these cases, the ventricular capture tests as described above will be performed first, then AF cycle length will be determined, and the two-stage atrial pacing scheme as described above will be performed. If delivery of the slow pacing phase of the two-stage atrial pacing scheme either will not be feasible or not stop the AF, the subject will be externally cardioverted under deep sedation as would have been done as common practice at the end of the ablation procedure. Next, during sinus rhythm pacing thresholds and impedances on all septal catheter electrodes will be determined.

[figure not shown]
Protocol deviations from what is stated above will be documented.

Figure 1: Study steps to be added to standard procedure.

STANDARD ABLATION PROCEDURE

AF SEPTAL PACING STUDY DURING STANDARD ABLATION PROCEDURE

*Patient is under deep sedation for whole procedure
§ If subject is still on AF

No follow-up data will be requested for the study.

Sponsor's representatives may provide support as required for the clinical study, including:

- Provide study training relevant and pertinent to the involvement of personnel conducting study activities and investigator responsibilities;
- Technical support during AF Septal Pacing procedure.

- Technical support at all visits under the supervision of a study investigator, but no data entry, shall be performed by Medtronic personnel or their representatives at sites;
- Provide clarification in case of need on correct completion and/or correction of CRFs;
- Monitoring and auditing activities;

The sponsor's representatives providing technical support during AF Septal Pacing procedure will be listed on the sponsor's technical support list.

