One reason why clinical studies are often non-conclusive, could be that they focus on AF frequency and burden, but few of them are aimed at evaluating the effect of AF pacing on the atrial tissue.⁹ More detail can be found in animal and human mapping experiments: although termination of AF by rapid pacing was not observed, the possibility of creating an area of local capture of the atrial tissue by rapid pacing of AF has been demonstrated.¹⁰⁻¹⁴ To overcome the limitations of human and animal experiments, a computer model of AF has been used to systematically simulate all existing ATP algorithms on AF and test all pacing locations.¹⁵ This systematic model-based testing of site rapid pacing of AF revealed that the septum was the only pacing site that yielded sporadic AF capture episodes in both atria, but this in general did not result in AF termination or permanent changes in AF patterns. Based on this result, a new dual-stage septal pacing has been developed in the computer model: rapid pacing was applied from the septal area following a dual-stage scheme: 1) rapid pacing for 10-30 s at pacing intervals 62-70% of AF cycle length (AFCL), 2) slow pacing for 1.5 s at 180% AFCL, initiated by a single stimulus at 130% AFCL.¹⁶ The proposed septal pacing algorithm could suppress AF reentries in a more robust way than classical single site rapid pacing and at an optimal pacing cycle length (64% AFCL) up to 29% of AF termination was observed in the computer model¹⁶. Septal pacing of AF is therefore proposed here as a simple and attractive approach since it may produce simultaneous bi-atrial stimulation using a single lead, without the need of complex methods for synchronizing multiple pacing sites.

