5.2.2. Secondary Endpoint(s)

To assess Localized Atrial Capture the following endpoints will be considered:

- The number of AF episodes in which local capture is recorded during atrial septal stimulation in at least one of the electrode positions
- The number of electrodes for which local capture is determined using pacing schemes with various pacing cycle lengths (PCL) for a duration of 10-30 seconds depending on when capture occurs, at the start of the scheme followed, if feasible, by slow pacing for 1.5 s at 180% AFCL, initiated by a single stimulus at 130% AFCL.
- The spatial extend of capture (assessed from the atrial electrograms recorded from the multipolar right atrial catheter and the multipolar coronary sinus catheter) to obtain local atrial capture obtained with septal pacing of AF, will be assessed off-line after the study procedure.

To assess whether AF termination can be obtained using a dual-stage septal pacing scheme, the surface ECG will be analyzed and the PCL and stimulation current used will be noted to measure the number of subjects in which the pacing scheme successfully terminates the AF episode.

6. Study Design

The AF Septal Pacing study is a non-randomized, non-controlled, acute, single-arm research study that will be conducted in up to three European centers.

Approximately 15 subjects with AF indicated for ablation of the pulmonary vein will be enrolled in the study. Participants will attend the Baseline visit and the Procedure visit. The baseline visit can be on the same day as the ablation procedure. Since it is an acute study, no follow-up visit will occur. The research procedure will be performed during an already scheduled ablation procedure. Subjects will be enrolled over a period of approximately 18 months.

The point of enrollment is the time when subject signs and dates the Informed Consent Form (ICF). At that point, the subject is considered included in the study.

Selection of subjects, treatment of subjects, and evaluation of study data are potential sources of bias. Methods incorporated in the study design to minimize potential bias include (but are not limited to):

- Patients will be screened to confirm eligibility for enrollment in accordance to the inclusion/exclusion criteria.
- Subject demographics will be collected at baseline on possible differences that may affect the primary objective.

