- All study clinicians, participating site personnel, and Medtronic personnel will be trained on their respective pertinent role of the study using standardized training materials.

No control group, no randomization and no blinding will be used in this Study.

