Next, atrial fibrillation will be induced by rapid atrial pacing, gradually elevating the atrial pacing rate until 1:1 atrial capture is lost. AF cycle length will be determined by recording the atrial electrogram on the septum. Stimulation on the septum from all electrodes starts at the current defined above, using various pacing cycle length (PCL), being percentages of AFCL and will last for 10 to 30 seconds, depending on when capture occurs, followed, if feasible, by slow pacing using an interval of 130% of AF for one cycle followed by 1.5 second of 180% of AF Cycle length at maximum output which did not induce ventricular capture (20 mA or lower). Multiple PCLs will be used to start the pacing sequence. During each stimulation sequence, corresponding to each PCL, atrial capture at each recording electrode will be assessed. The optimal parameters for stimulation will be used to determine local capture for all electrodes.

When the subject will still be in AF after successful pulmonary vein isolation the ventricular capture tests will be performed first during atrial fibrillation (as described above for subject in sinus rhythm). Then, AF cycle length will be determined and

the two-stage atrial pacing scheme as described above will be performed. If delivery of the two-stage atrial pacing scheme either will not be feasible or not stop the AF, the subject will be externally cardioverted under deep sedation as would have been done as common practice at the end of the ablation procedure. Next, during sinus rhythm pacing thresholds and impedances on all septal catheter electrodes will be determined.

To assess if the two-stage pacing scheme can terminate AF, the surface ECG will be analyzed and PCL and stimulation current will be noted.

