14.1. Sample Size

As this is a feasibility study, no formal statistical hypotheses are being tested and no sample size calculation was performed.

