AF Termination Scheme: evaluate if AF termination was observed during the experimental atrial septal pacing scheme from multiple electrodes on the interatrial septum. Acute procedural AF termination was defined as termination of AF to SR or a regular atrial tachycardia/flutter during the experimental pacing procedure without re-initiation of atrial fibrillation during the experimental pacing scheme.

AF termination will be described as the count and frequency of any AF termination
Subgroup descriptions and summary of atrial capture and AF termination will be done for:

- Atrial fibrillation group (SR vs AF group)
- Catheter type (Achieve vs. Lasso or other)
- Anatomical electrode position
- Atrial Cycle Length

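### AF terminations are counted during pacing of freshly induced AF with no unpaced reference, so spontaneous stops cannot be told from stops caused by the scheme

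*Protocol*

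**What the plan says.** **Design.** Protocol 6 states "Approximately 15 subjects with AF indicated for ablation of the pulmonary vein will be enrolled in the study" and "No control group, no randomization and no blinding will be used in this Study". Protocol 14.1 adds that "no formal statistical hypotheses are being tested and no sample size calculation was performed".

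**Rhythm at the start.** After pulmonary vein isolation, Protocol 10 expects that "In most cases the patient will be in sinus rhythm". In those subjects AF is induced by rapid atrial pacing. Then "AF cycle length will be determined, during 1 minute of atrial fibrillation using the ablation catheter electrodes", after which septal pacing begins. Protocol 10.3 describes the same step without a duration and at another site: "AF cycle length will be determined by recording the atrial electrogram on the septum".

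**Exposure.** Protocol 10.3 gives 10 to 30 s of rapid pacing per sequence, then, if feasible, one cycle at 130% and 1.5 s at 180% of AF cycle length. Several pacing cycle lengths are tried. The number of sequences is not stated.

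**Endpoint.** Protocol 5.2.2 counts the subjects in whom the scheme succeeds in ending AF. SAP 8.7.2 counts a change from AF to sinus rhythm or to a regular atrial tachycardia or flutter during the experimental pacing procedure, provided AF does not restart during the scheme. The analysis is one line: "AF termination will be described as the count and frequency of any AF termination". Results are also described for the SR and AF groups.

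**Data.** Electrograms are recorded throughout (Protocol 7.1). Protocol Table 2, the procedure data list in Protocol 10.5 and SAP appendix Tables 5 and 6 contain no item for inductions, AF onset or offset, or AF that ended before pacing. Tables 5 and 6 name AF termination in their titles but list no termination field. The disposition list in SAP 8.1.1 has no category for AF that ended before pacing.

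**The concern.** AF that was induced a minute or so earlier may stop without help. If it stops inside a pacing run, the SAP counts it and the protocol endpoint credits the scheme. With no control group, the only available guide to the background is how often induced AF stops while unpaced. The procedure provides such an observation period, but the plan neither tabulates nor reports what happens in it.

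Repeated runs make this worse, because each one adds time in which a spontaneous stop would be counted. Protocol 7.3 says subjects are enrolled to test whether the algorithm can terminate AF, so readers will take the count as evidence on that question. At stake is the interpretation of a secondary endpoint. The primary endpoint, electrode stability, is not affected.

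**Working it through.** The plan gives no figure to reproduce: there is no sample size calculation, no target termination rate and no spontaneous rate. The check asks how many terminations would be counted if pacing did nothing.

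**Inputs from the documents**
- Subjects: about 15, most of them induced (Protocol 6 and 10). All 15 are taken as induced below, which is an upper case.
- Shortest run: 10 + 1.5 = 11.5 s. Longest run: 30 + 1.5 = 31.5 s (Protocol 10.3). The single cycle at 130% is ignored.

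**Assumptions not in the documents**
- Spontaneous risk p per minute of induced AF: 5%, 10% or 20%, constant over time.
- Number of runs: k = 3.

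**Chance of a counted stop per subject with no pacing effect**

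q = 1 − (1 − p)^(k × run length in s / 60)

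The exponent is 3 × 11.5/60 = 0.575 for short runs and 3 × 31.5/60 = 1.575 for long runs.

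| p per minute | q, 11.5 s runs | q, 31.5 s runs | Expected of 15 (15q) | Chance of at least one in 15, 1 − (1 − q)^15 |
|---|---|---|---|---|
| 5% | 2.9% | 7.8% | 0.4 to 1.2 | 36% to 70% |
| 10% | 5.9% | 15.3% | 0.9 to 2.3 | 60% to 92% |
| 20% | 12.0% | 29.6% | 1.8 to 4.4 | 85% to over 99% |

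Over this grid, q runs from about 3% to about 30%.

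**What the unpaced observation can supply (exact Poisson 95% limits)**
- One subject, one minute, no event: 0 to 3.69 per minute. One event: 0.025 to 5.57 per minute. Neither is informative.
- Fifteen subject-minutes pooled, no event: 0 to 3.69/15 = 0.246 per minute. This corresponds to 0 to 1 − exp(−0.246 × 0.525) = 12.1% per 31.5 s run.
- Fifteen subject-minutes, two events: 0.016 to 0.482 per minute, or 0.8% to 22.3% per 31.5 s run.
- If only 12 subjects were induced (an assumed figure), no event in 12 minutes gives 0 to 3.69/12 = 0.307 per minute.

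**Why the comparison must not be paired**

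An episode reaches pacing only if AF lasted through the unpaced period, so that period contains no termination by construction. With p = 20%, three 31.5 s runs and no pacing effect, a paired display shows 0 unpaced stops against an average of 4.4 of 15 paced stops. A 6:0 split, which gives a two-sided exact p of 2 × (1/2)^6 = 0.031, or a more extreme one occurs in about 26% of simulated studies. The background information lies in the inductions that stopped before pacing. With p = 20%, about 3.7 are expected in 15 subjects if AF were re-induced until it lasted a minute. The documents do not describe such a re-induction step.

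**The case against.** The study is openly descriptive, tests no hypothesis and makes termination a secondary endpoint, evaluated if feasible. The SAP wording is also more cautious than the protocol's: it asks whether termination was observed during the scheme. All of this stands, and it limits the weight of the point. It does not help a reader judge a count of, say, 3 of 15.

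Part of the remedy is already planned. SAP 8.7 and 8.7.2 describe results by initial arrhythmia and by SR and AF group, which separates induced from ongoing AF. SAP 8.1.1 counts subjects who had the overdrive test, so subjects who were never paced are visible, though not the reason. The electrograms are kept, so a reader who inferred that evidence of self-termination is lost would go too far: it is stored, but not tabulated. The CRF itself is not among the documents.

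Four further readings are tempting and are not supported:

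- **That the unpaced minute gives each subject's own spontaneous rate.** An interval of 0 to 3.69 per minute after no event rules that out. Only a pooled rate is possible.
- **That chance alone reproduces the modelling result.** Protocol 4.1 reports "up to 29% of AF termination was observed in the computer model", and the 29.6% cell above looks like a match. That cell is an assumed any-of-three-runs chance at full run length (12.0% with short runs), whereas the model figure belongs to one optimal cycle length. Per 31.5 s run, p = 20% gives 1 − 0.8^0.525 = 11.1%. Reaching 29% in one run would need 1 − 0.71^(1/0.525), about 48% per minute. The plan does not make 29% a success threshold.
- **That the minute is fixed throughout the protocol.** Protocol 3 and 10 state it, but 10.3 gives no duration.
- **That the change is free.** It needs no added AF time, but it does need CRF fields and SAP text.

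**Conclusion.** The point holds as a matter of interpretation. As planned, a termination in induced AF cannot be attributed either to the scheme or to chance. Under the stated assumptions (constant risk of 5% to 20% per minute, three runs of 11.5 to 31.5 s), about 3% to 30% of induced subjects would be counted with no pacing effect. The width of that range reflects how little the documents say about the spontaneous rate, the number of runs and their length.

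A pooled unpaced rate would help, within limits. It is coarse. It may overstate the background during pacing if the risk falls with time since induction. It is valid only if inductions that ended before pacing are included. It would qualify the count and would not turn the study into a controlled one. The change is worth making because it is cheap; it is not a reason to doubt the primary objective.

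**What to change.** 1. **CRF and SAP data tables.** Log every induction with time of AF onset and offset, whether AF ended before pacing, and whether and when it ended during a run. The continuous recordings can supply these times. Add the missing termination field to SAP Tables 5 and 6.
2. **SAP 8.1.1.** Add a disposition category for AF that ended before pacing.
3. **SAP 8.7.2.** Within the SR and AF groups already planned, report pooled terminations per minute of unpaced AF over all inductions beside terminations per minute of paced AF, each with an exact confidence interval. Do not present this as a within-subject or paired comparison. State that terminations in induced AF are not attributed to pacing without this reference.
4. **Limits to state.** Say that the reference is imprecise, that it may overstate the background if the risk declines after induction, and that paced episodes have survived the unpaced period.
5. **Protocol 10 and 10.3.** Reconcile the two descriptions of how AF cycle length is recorded (1 minute with the ablation catheter; no duration with the septal electrogram). The unpaced exposure depends on this.

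The cost is a few CRF fields, some SAP text and the reading of recordings already made. No extra time in AF is required. The drawback is an imprecise reference, which the exact intervals will show.
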